12.5 ECG Data

ECG data will be collected by using a digital 12-lead ECG machine throughout the study.

The absolute value and change from baseline in 12-Lead ECG parameters (PR, QRS, QT) will be summarized descriptively for the SAF.

The number and percentage of patients with any clinically significant findings reported by the investigator will be tabulated by scheduled time-point. The absolute 12-Lead ECG parameters will be listed by patient and visit along with ECG findings.

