3. Medical history includes demographic information and medical and surgical history. Cancer history includes current cancer diagnosis, treatment regimens (regimen, doses, start and stop dates), and best response for each regimen.
4. A complete physical exam is required at the Screening and the Post-Treatment Safety Assessment visits. Otherwise, a symptom-directed physical exam should be performed where indicated.
5. ECOG (Eastern Cooperative Oncology Group) performance status ([Appendix 1](#)).
6. Vital signs include blood pressure, pulse, temperature, and respirations. On Day 1 of each cycle, vital signs will be recorded prior to INXN-1001 dosing and hourly for the first two hours after INXN-2001 dosing. Blood pressure is to be monitored closely to prevent hypotension after administration of INXN-1001. Blood pressure assessment is required on Day 3 or Day 4 for Cycle 1 and Cycle 2. Subjects must be instructed to maintain adequate oral hydration on and in between dosing days; sites must closely monitor subjects' hydration status.
7. Monitoring and recording of adverse events (AEs) and serious adverse events (SAEs) will be conducted throughout the study. AEs/SAEs that occur following informed consent until the Post-Treatment Safety Assessment must be recorded on the AE CRF. In addition, all SAEs must be reported by the investigator or designee within 24 hours of becoming aware of the event, from the time of informed consent through 30 days after the last dose of study drug, regardless of the initiation of any new anti-cancer therapy.

8. Concomitant medication information, including blood products, vitamins and other supplements will be collected for the time period beginning 28 days prior to the first dose of study drug, through the Follow-Up Tumor Assessment visit.
9. Females of childbearing potential will have a serum pregnancy test at the Screening visit and a urine pregnancy test on the first day of each treatment cycle, prior to administration of INXN-1001.
10. Hematology tests include: complete blood count and white blood cell count, differential white blood cell count, red blood cell count, hematocrit, hemoglobin, red blood cell indices, reticulocyte count, MCV (mean corpuscular volume) and platelet count. PTT (partial thromboplastin time) and INR (international normalized ratio) will also be evaluated.

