11. Serum chemistry tests include: aspartate transaminase (AST), alanine transaminase (ALT), lactate dehydrogenase (LDH), alkaline phosphatase (ALP), creatinine, total bilirubin, total protein, albumin, blood urea nitrogen, glucose, sodium, potassium, chloride, calcium, phosphorus and bicarbonate.
12. Urinalysis panel (dipstick) includes: appearance, pH, specific gravity, glucose, protein/albumin, blood, ketones, bilirubin, nitrates, and leukocyte esterase. In addition, a microscopic exam for casts, crystals, and cells may be done if clinically indicated.
13. Standard, single 12-lead ECG at screening, 2½ to 3 hours after INXN-1001 dosing (prior to INXN-2001 injection) on Day 1 of each cycle, and at the Post-Treatment Safety Assessment visit.
14. Serum tryptase level will be obtained upon the occurrence of a suspected injection and/or hypersensitivity reaction. Otherwise, this test is not required at any other time.
15. For subjects who meet inclusion and exclusion criteria. Centralized registration of eligible subjects will be completed according to a process defined by the sponsor.
16. Blood sample for analysis of antibody responses to the adenovirus and/or the RTS█ components, and antibodies to melanoma-associated antigens. Please refer to the laboratory manual for details regarding sample processing and shipment.
17. Blood samples for cytokine profiling. Please refer to the laboratory manual for details regarding sample processing and shipment.
18. Appropriate cancer staging procedures should be performed during screening. For the purpose of this clinical trial, the following imaging is expected at screening:
 - a. CT of the chest, and CT (or MRI) of the abdomen and pelvis
 - b. MRI (or CT) of the brain if brain metastasis are known or suspected
 - c. CT or MRI of other anatomical regions as clinically indicated

For subjects with measurable lesions, target lesions should be selected and measured as per RECIST 1.1 guidelines. Lesions that will be/are injected with INXN-2001 and/or biopsied should not be selected as target lesions, but should be measured (if measureable).

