8.4.2.11 Electrocardiogram (ECGs)

A standard, single 12-lead ECG for local safety assessment will be done at screening, 2½ to 3 hours after INXN-1001 dosing (prior to INXN-2001 injection) on Day 1 of each cycle, and at the Post-Treatment Safety Assessment visit. The ECGs will be used to evaluate the QT/QTc interval.

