| 12.6 | ECOG Status..... | 20 |
| 12.7 | Physical Examination | 20 |
| 13.0 | Interim Analysis..... | 20 |
| 14.0 | Changes to Planned Methodology | 20 |
| 15.0 | Tables, Figures and Listings | 22 |
| 15.1 | List of Tables..... | 22 |
| 15.2 | List of Figures..... | 23 |
| 15.3 | List of Listings..... | 23 |

Abbreviations

| Abbreviation | Meaning |
|--------------|--|
| ADV | Adenoviral vector shedding |
| AE | Adverse Event |
| ACEV | Activity Evaluable Population |
| ATC | Anatomical Therapeutic Chemical |
| bpm | Beats per minute |
| BMI | Body mass index |
| BRAF | Human gene that makes a protein called B-Raf |
| cm | Centimeter |
| CR | Complete Response |
| CTCAE | NCI Common Terminology Criteria for Adverse Events |
| CTL | Cytotoxic T Lymphocytes |
| DLT | Dose-limiting Toxicity |
| ECG | Electrocardiogram |
| FNA | Fine Needle Aspirate |
| GGT | Gamma Glutamyl Transferase |
| Hgb | Hemoglobin |
| INXN-1001 | INXN-1001 (Oral Activator Ligand) |
| INXN-2001 | INXN-2001 (Ad-RTS-hIL-12) |
| kg | Kilogram |
| KM | Kaplan-Meier |
| lb | Imperial pounds (weight) |
| MedDRA | Medical Dictionary for Regulatory Activities |
| mg | Milligram |
| MTD | Maximum Tolerated Dose |
| PB | Punch Biopsy |
| PBMC | Peripheral Blood Mononuclear Cells |
| PD | Progressive Disease |
| PFS | Progression-free Survival |
| PK | Pharmacokinetic |
| PR | Interval measured from the beginning of the P wave to the beginning of the QRS complex |
| PR | Partial Response |
| PT | Preferred term |
| PTSA | Post Treatment Safety Assessment |
| QRS | Complex containing Q wave, R wave and S wave |
| QT | Interval between start of the Q wave and the end of the T wave |
| RBC | Red Blood Cell Count |
| RECIST | Response Evaluation Criteria In Solid Tumors |

| Abbreviation | Meaning |
|--------------|----------------------------------|
| SAE | Serious Adverse Event |
| SAF | Safety Population |
| SAP | Statistical Analysis Plan |
| SAS | Statistical Analysis System |
| SD | Standard Deviation |
| SD | Stable Disease |
| SOC | System Organ Class |
| SRC | Safety Review Committee |
| TEAE | Treatment-Emergent Adverse Event |
| Tregs | T-regulatory cells |
| vp | Viral particles |
| WHO | World Health Organization |

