9.2 Baseline

Unless otherwise specified, baseline is the last observation before the first study drug administration.

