| Table 14.3.3.2 | Shift from Baseline to Worst Post-Baseline Value (Low/High) for Hematology Parameters | Safety Population |
| Table 14.3.3.3 | Summary of Absolute and Change from Baseline Value for Urinalysis Results | Safety Population |
| Table 14.3.4 | Summary of Absolute and Change from Baseline Value for Vital Sign Parameters | Safety Population |
| Table 14.3.5.1 | Summary of Absolute and Change from Baseline Value for ECG Parameters | Safety Population |
| Table 14.3.5.2 | Summary of ECG Findings | Safety Population |

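### The protocol takes ECGs to evaluate QT/QTc, but the SAP's quantitative ECG summary has only uncorrected QT, compared with a screening baseline and with no heart-rate correction

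*SAP*

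**What the plan says.** Protocol 8.4.2.11 describes a single 12-lead ECG for local safety assessment and gives its use: "The ECGs will be used to evaluate the QT/QTc interval". ECGs are scheduled at screening, on Day 1 of every cycle and at the Post-Treatment Safety Assessment visit. Footnote 13 of protocol Table 2 places the Day 1 ECG at 2½ to 3 "hours after INXN-1001 dosing (prior to INXN-2001 injection) on Day 1 of each cycle".

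SAP 12.5 sets the quantitative analysis: "The absolute value and change from baseline in 12-Lead ECG parameters (PR, QRS, QT) will be summarized descriptively for the SAF". The SAP abbreviations define QT as "Interval between start of the Q wave and the end of the T wave", which is the uncorrected interval, and have no entry for QTc. The one quantitative ECG output is Table 14.3.5.1, "Summary of Absolute and Change from Baseline Value for ECG Parameters". SAP 12.5 adds a qualitative output: "The number and percentage of patients with any clinically significant findings reported by the investigator will be tabulated by scheduled time-point".

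SAP 12.5 sets no ECG baseline, so the general rule in SAP 9.2 applies: "baseline is the last observation before the first study drug administration". Heart rate appears in the SAP only as a vital sign (12.4). For Day 1, footnote 6 of protocol Table 2 says that "vital signs will be recorded prior to INXN-1001 dosing and hourly for the first two hours after INXN-2001 dosing".

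**The concern.** QT depends on heart rate, and QTc exists to remove that dependence. Without a correction, the change in QT between two ECGs is the sum of any repolarisation effect and the shift produced by any rate difference. Table 14.3.5.1 cannot separate the two. The error can go either way: a faster rate on Day 1 hides a real prolongation, and a slower rate creates a false one.

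Safety is the primary objective, ECGs are a named safety parameter, and the trial is meant to inform the INXN-1001 dose and regimen. As planned, the interval that the protocol says these ECGs are for has no quantitative QTc evaluation.

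**Working it through.** The documents give no QT, QTc or heart-rate figure, so there is none to reproduce. The check sets the texts side by side and then illustrates the size with assumed values.

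**1. Which ECG is the baseline?** Protocol Table 2 marks one ECG before dosing, in the Day -28 to -7 screening column. The Day 1 ECG is post-dose. Under SAP 9.2 the scheduled baseline is therefore the screening ECG, and SAP 9.3 also falls back on screening values. The comparison is between a screening ECG up to 28 days old and one taken 2½ to 3 hours after a dose given in the fed state. Nothing in the schedule holds heart rate constant between them.

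**2. Can vital-sign heart rate stand in on Day 1?**
- The ECG is at 2.5 to 3.0 h after INXN-1001 and before the injection.
- The injection is due at 3 h ± 30 min, i.e. 2.5 to 3.5 h.
- The first hourly vital signs after the injection fall at 3.5 to 4.5 h. As the ECG precedes the injection, they are at least 1 h after it.
- The preceding set is pre-dose, at least 2.5 h before the ECG.

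No Day 1 vital signs are specified at the ECG time.

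**3. How large could the distortion be?** Assumed: Fridericia, QTcF = QT / (60/HR)^(1/3), starting at QT 400 ms and 70 bpm.

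QTcF = 400 / (60/70)^(1/3) = 421.1 ms.

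Raw QT at constant QTcF is 421.1 × (60/HR)^(1/3):

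| Heart rate (bpm) | Raw QT (ms) | Change from 400 (ms) |
|---|---|---|
| 60 | 421.1 | +21.1 |
| 75 | 390.9 | -9.1 |
| 80 | 382.6 | -17.4 |
| 90 | 367.9 | -32.1 |

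A true QTcF rise of d ms gives no change in raw QT when HR = 60 × ((421.1 + d)/400)^3:
- d = 10: 75.1 bpm, about 5 bpm above the start.
- d = 20: 80.5 bpm, 10.5 bpm above the start.

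Other starting points: from QT 420 at 60 bpm, a 10 ms rise is hidden at 64.4 bpm (+4.4). From QT 380 at 80 bpm, it is hidden at 85.9 bpm (+5.9).

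**4. Does the formula matter?** With QTc assumed at 390 to 430 ms and heart rate going from 70 to 80 bpm, raw QT falls by 16 to 18 ms under Fridericia and by 23 to 26 ms under Bazett, with no change in QTc. The size differs but the direction is the same.

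**5. What if there is no systematic rate change?** Near the start, the slope is QT/(3 × HR) = 400/210 = 1.905 ms per bpm. The standard error that rate variation alone adds to a group's mean QT change is 1.905 × SD/√n, where SD is the assumed between-patient SD of the heart-rate change:

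| SD (bpm) | n = 4 | n = 2 |
|---|---|---|
| 5 | 4.8 ms | 6.7 ms |
| 10 | 9.5 ms | 13.5 ms |

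SAP 1.0 gives 2 to 4 treated patients per dose group.

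**The case against.** The strongest reply is that protocol 8.4.2.11 describes local safety assessment, which can be read as evaluation at the site. Protocol 10.3.2 promises no QTc table; it says clinically significant ECG changes are captured as adverse events. On that reading SAP 14.0 had no planned analysis to declare as dropped. This has some force, and it weakens the complaint about SAP 14.0. It does not rescue the table. Once the SAP tabulates change in QT, the result should be interpretable, and the investigator findings and adverse events are qualitative. Neither document states a QTc criterion for them. Adverse events are graded by CTCAE v4.03, and whether that supplies a threshold cannot be settled from the documents.

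Other replies stand in part:
- Vital signs and ECG share the screening window and the post-treatment visit, so heart rate may give context there. The timing gap in the working is a Day 1 argument only.
- Each phase has an Overall column. With all 13 treated patients contributing, the added standard error is 1.905 × 5/√13 = 2.6 ms to 1.905 × 10/√13 = 5.3 ms, below the dose-group values. A systematic rate shift would not shrink with n.
- Correcting for rate does not make the screening baseline any more recent. That limit stays.
- The analysis is descriptive and the groups are tiny. This argues for making the patient listing the main output, not for leaving QT uncorrected.

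**Conclusion.** The concern holds. Protocol 8.4.2.11 names QT/QTc; the SAP analyses raw QT alone and does not explain the difference. The scheduled baseline leaves heart rate free to differ, and Day 1 vital signs are not taken at the ECG time.

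Under the assumed Fridericia values, a difference of about 4 to 6 bpm is enough to cancel a true 10 ms QTc rise, and one of 10 bpm moves raw QT by roughly 17 to 21 ms with no QTc effect. These figures show sensitivity; they do not predict what this trial will find, because its heart-rate differences are unknown. The conclusion that raw QT change cannot be read as a QTc assessment does not depend on the chosen starting values or on Fridericia rather than Bazett. The plan should be changed, though the point does not put the trial's main safety tabulations in doubt.

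**What to change.** In SAP 12.5, Table 14.3.5.1 and Listing 16.2.10:
- Derive QTc by a named formula, for example Fridericia, from QT and the RR interval or heart rate of the same ECG.
- Summarise absolute value and change from baseline for QTc and ECG heart rate next to PR, QRS and QT.
- List QTc and ECG heart rate by patient and visit. With 2 to 4 patients per dose group this listing is the main output; counts by QTc category are optional.
- State in 12.5 that the ECG baseline is the screening ECG.

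The cost is one derived variable and extra rows in an existing table and listing. The documents do not show whether the eCRF holds ECG heart rate or RR. If it does not, the values would have to be retrieved from existing ECG records for 26 patients (13 per phase) across the sites, planned at about 8 to 12. If they cannot be retrieved, one sentence in SAP 14.0 should state that QTc was not evaluated and that change in raw QT is not a QTc assessment. No patient visit or study procedure changes.

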12.6 ECOG Status

ECOG status will be collected throughout the study.

ECOG status will be listed.

12.7 Physical Examination

Physical examinations will be performed throughout the study. Details of physical examinations will be listed.

13.0 Interim Analysis

There is no planned interim analysis.

14.0 Changes to Planned Methodology

The following changes will be made to the planned analysis based on the final number of enrolled subjects:

Section 10.3.3 of the Protocol states that following completion of the study, best response will be determined for each subject in accordance with RECIST v.1.1 guidelines and the objective response rate presented for each dose cohort. Progression-free survival and durability of response will be determined using Kaplan-Meier methodology.

Objective response, BOR and PFS will be determined and listed for each individual subject. Additionally BOR and PFS will be tabulated. Objective response rate and duration of response will not be calculated.

Section 10.3.3 of the Protocol also states that as a supplement to the standard RECIST v1.1 guidelines established to evaluate anti-tumor responses to chemotherapeutic agents, the sponsor will be analyzing anti-tumor response by assessing total tumor burden over time. Tumor burden activity was not collected and as such no summaries will be included for this data.

Section 10.3.3 of the Protocol also states that at each time point, the change in immunologic response (CTL and Treg frequency in blood) from baseline and from the preceding time point will be correlated with the INXN-1001 dosage level. In addition, tumor punch biopsies or FNAs will be examined for genomic changes due to IL-12 expression, presence of injected adenovirus and CTL frequency, Treg and MDSC frequency, and other immunological markers. The change in each measure from baseline and from the preceding biopsy will be correlated with the INXN-1001 dose used in the each cohort.

Immunologic and biological response marker data will be listed only.

15.0 Tables, Figures and Listings

Tables and listings will be presented landscape. A font size of 8 and a font of courier new will be used throughout for tables and listings. Tables and listings will be provided as a bookmarked pdf.

The patient subset being utilized in the table will be indicated in the table title. Page numbers and dates of production will be included in an appropriate place at the bottom of the output. Listings which support the table will also be detailed in an appropriate place at the bottom of the output.

Tables will only be generated where there is sufficient data to warrant the inclusion of the table.

15.1 List of Tables

| Table Number | Table Title | Population |
|----------------|--|-------------------------------|
| Table 14.1.1 | Patient Disposition | Safety Population |
| Table 14.1.2 | Protocol Deviations | Safety Population |
| Table 14.1.3 | Demography | Safety Population |
| Table 14.1.4 | Medical History | Safety Population |
| Table 14.1.5 | Oncology History | Safety Population |
| Table 14.1.6 | Oncology History – Time Since Diagnosis, Disease Status and Staging | Safety Population |
| Table 14.1.7 | Previous Medications | Safety Population |
| Table 14.1.8 | Concomitant Medications | Safety Population |
| Table 14.1.9 | Prior Cancer Treatment | Safety Population |
| Table 14.2.1 | Best Overall Response | Activity Evaluable Population |
| Table 14.2.2 | Progression-free Survival (Kaplan-Meier Analysis) | Activity Evaluable Population |
| Table 14.3.1 | Exposure | Safety Population |
| Table 14.3.2.1 | Overall Adverse Event Summary | Safety Population |
| Table 14.3.2.2 | Adverse Events by System Organ Class and Preferred Term | Safety Population |
| Table 14.3.2.3 | Treatment Emergent Adverse Events by System Organ Class and Preferred Term | Safety Population |

| Table Number | Table Title | Population |
|-----------------|---|-------------------|
| Table 14.3.2.4 | Drug-Related Treatment Emergent Adverse Events by System Organ Class and Preferred Term | Safety Population |
| Table 14.3.2.5 | Serious Adverse Events by System Organ Class and Preferred Term | Safety Population |
| Table 14.3.2.6 | Drug-Related Serious Adverse Events by System Organ Class, Preferred Term | Safety Population |
| Table 14.3.2.7 | CTC Grade 3 or greater Adverse Events by System Organ Class, Preferred Term | Safety Population |
| Table 14.3.2.8 | Drug-Related CTC Grade 3 or Greater Adverse Events by System Organ Class and Preferred Term | Safety Population |
| Table 14.3.2.9 | Adverse Events Leading to Discontinuation by System Organ Class and Preferred Term | Safety Population |
| Table 14.3.2.10 | Summary of Injection Site Reactions | Safety Population |
| Table 14.3.2.11 | Summary of Injection Site Reactions by Type and Severity | Safety Population |
| Table 14.3.2.12 | Summary of Injection Site Reactions by Type and Relationship | Safety Population |
| Table 14.3.3.1 | Shift from Baseline to Worst Post-Baseline Value (Low/High) for Clinical Chemistry Parameters | Safety Population |
| Table 14.3.3.2 | Shift from Baseline to Worst Post-Baseline Value (Low/High) for Hematology Parameters | Safety Population |
| Table 14.3.3.3 | Summary of Absolute and Change from Baseline Value for Urinalysis Results | Safety Population |
| Table 14.3.4 | Summary of Absolute and Change from Baseline Value for Vital Sign Parameters | Safety Population |
| Table 14.3.5.1 | Summary of Absolute and Change from Baseline Value for ECG Parameters | Safety Population |
| Table 14.3.5.2 | Summary of ECG Findings | Safety Population |

15.2 List of Figures

No Figures are required for this study.

15.3 List of Listings

Listings will be sorted by patient number within Phase, group (for Phase II patients) and dose cohort.

| Listing Number | Listing Title | Population |
|-----------------------|---|-------------------|
| Listing 16.2.1.1 | Patient Disposition | Safety Population |
| Listing 16.2.1.2 | Inclusion and Exclusion Criteria | Safety Population |
| Listing 16.2.1.3 | Eligibility | Safety Population |
| Listing 16.2.2 | Protocol Deviations | Safety Population |
| Listing 16.2.3 | Population Allocation | Safety Population |
| Listing 16.2.4.1 | Demography and Baseline Characteristics | Safety Population |
| Listing 16.2.4.2 | Medical History | Safety Population |
| Listing 16.2.4.3 | Oncology History | Safety Population |
| Listing 16.2.4.4 | Prior Cancer Therapy | Safety Population |
| Listing 16.2.4.5 | Prior Medications | Safety Population |
| Listing 16.2.4.6 | Concomitant Medications | Safety Population |
| Listing 16.2.5.1 | Study Drug Administration | Safety Population |
| Listing 16.2.5.2 | Drug Dosing Schedule | Safety Population |
| Listing 16.2.5.3 | Overall Study Drug Exposure | Safety Population |
| Listing 16.2.5.4 | Pharmacokinetic Sampling | Safety Population |
| Listing 16.2.6.1 | Tumor Assessments | Safety Population |
| Listing 16.2.6.2 | Overall Tumor Assessments | Safety Population |
| Listing 16.2.6.3 | Best Overall Response and Progression-free Survival | Safety Population |
| Listing 16.2.6.4 | PBMC | Safety Population |
| Listing 16.2.6.5 | Serum Antibody Responses | Safety Population |
| Listing 16.2.6.6 | Cytokine Profiling Responses | Safety Population |
| Listing 16.2.6.7 | Serum Tryptase Responses | Safety Population |
| Listing 16.2.6.8 | T cells | Safety Population |
| Listing 16.2.6.9 | NK cells | Safety Population |
| Listing 16.2.6.10 | T-regulatory (Tregs) | Safety Population |
| Listing 16.2.6.11 | Adenoviral Vector Shedding | Safety Population |
| Listing 16.2.7.1 | Adverse Events | Safety Population |
| Listing 16.2.7.2 | Treatment Emergent Adverse Events | Safety Population |

| Listing Number | Listing Title | Population |
|-----------------------|---|-------------------|
| Listing 16.2.7.3 | Treatment Emergent Serious Adverse Events | Safety Population |
| Listing 16.2.7.4 | Treatment Emergent Adverse Events Related to Study Drug | Safety Population |
| Listing 16.2.7.5 | Treatment Emergent Adverse Events Leading to Withdrawal | Safety Population |
| Listing 16.2.7.6 | Treatment Emergent Adverse Events Leading to Death | Safety Population |
| Listing 16.2.7.8 | Injection Reaction | Safety Population |
| Listing 16.2.8.1 | Laboratory Reference Ranges | Safety Population |
| Listing 16.2.8.2 | Clinical Chemistry | Safety Population |
| Listing 16.2.8.3 | Hematology | Safety Population |
| Listing 16.2.8.4 | Urinalysis Data | Safety Population |
| Listing 16.2.8.5 | Pregnancy Test | Safety Population |
| Listing 16.2.9 | Vital Signs | Safety Population |
| Listing 16.2.10 | ECG Data | Safety Population |
| Listing 16.2.11 | ECOG Status | Safety Population |
| Listing 16.2.12 | Physical Examination | Safety Population |
| Listing 16.2.13 | Visit Dates | Safety Population |
| Listing 16.2.14 | Photo Catalog | Safety Population |
| Listing 16.2.15 | Waiver | Safety Population |
| Listing 16.2.16 | Adenoviral Vector Shedding | Safety Population |
